4.2 Exclusion Criteria

• Those with a comorbidity of other urological abnormalities or serious diseases

(e.g. hypospadias, cryptorchidism, posterior urethral valves, vesicoureteral reflux, neurogenic bladder, urological tumours, urinary stones, bladder and urethral injuries, etc.).

• Those with a comorbidity of neurological disorders (e.g. epilepsy, spinal cord injury, spinal cord dysplasia, spinal cord embolism syndrome, multiple sclerosis, autism spectrum disorder, etc.).

• Those with a comorbidity of severe heart disease, abnormal liver or kidney function, lung disease, skeletal deformities, severe gastrointestinal disease, or inherited metabolic disorders.

- Those with a history of gastrointestinal surgery and urinary tract surgery.
- Those with chronic constipation.

• Those taking anticonvulsant and antiepileptic drugs, hormones, antituberculosis drugs.

• Those have a previous history of hypercalcemia, hyperphosphatemia with renal rickets.

- Those have a history of hematuria and urinary tract infection within the last 1 year.
 - Those have a history of allergy or allergic disease to vitamin D preparations.
- Those Participate in other clinical studies at the time of consultation or during the follow-up of other clinical studies.
- Any condition that could cause urinary symptoms or interfere with assessment of efficacy parameters.
 - Those unwilling to participate in this study.

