5. STUDY INTERVENTIONS

5.1 Interventions, Administration, and Duration

During the eight-week treatment period, the study was divided into three intervention groups, and each patient received follow-up care from an outpatient physician every four weeks. Participants in each intervention group will be required to attend a 30-minute SU program per session.

Children assigned to the VDS+SU group will receive high-dose VDS (800 IU, three times per day) in addition to the biweekly SU course.

Children in the SOL+SU group will receive treatment with solifenacin succinate (5 mg once daily, with a maximum dose of 10 mg per day), in addition to the SU course.

Participants in the SU group only attend regular SU meetings, which provide basic information and an explanation of the disease, guidance on behavioral changes and lifestyle advice, registration of urinary habits using a bladder diary, as well as support and encouragement from caregivers.

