6.2 Description of Evaluations

6.2.1 Screening Evaluation

Eligible participants will be identified at the Outpatient Department of Urology, Children's Hospital of Chongqing Medical University. Patients will be further screened for eligibility by answering screening questions in a questionnaire (i.e., excluding exclusion criteria).

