6.2.1.2 Screening

Before the interventions begin, a screening assessment must be completed to determine eligibility. Medical records will be reviewed to identify patients who meet the relevant inclusion criteria and do not meet any exclusion criteria. These criteria will be confirmed at the time of enrollment through a questionnaire.

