6.2.2.3 Randomization

After completing a comprehensive baseline assessment and meeting the eligibility

criteria, eligible participants will be randomized into one of three different intervention groups. To ensure the highest standard of allocation concealment, the randomization process of this clinical trial will be executed by a designed computer program developed by a project staff member who is not involved in the execution and statistical analysis of this study. The allocation will be securely hidden in sequentially numbered sealed envelopes, which will be entrusted to an inpatient doctor who is not involved in the trial.

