9.3.1 Intention-to-treat (ITT) analysis

For outcomes that are continuous variables, which are numerical and can take any value within a range, we will use the ITT approach, which is a way of comparing the groups based on their original random assignment to a treatment, regardless of what treatment they actually received or completed. This helps to avoid bias from factors that may influence the results, such as dropout, which is when subjects leave the study before it ends, or crossover, which is when subjects switch to a different treatment than they were assigned to. The ITT approach is also simpler than other ways of analyzing the data that need to consider whether the subjects followed the treatment as planned or not.

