9.3.3 Safety analysis set

For safety analysis, which is when we assess the safety and side effects of the treatment, we will use the SS set, which is a subset of all patients who took at least one dose of the study drug and have safety records in the database. The database is where we store and manage our data electronically. We will only use measured values for this analysis, which are values that we actually observed and recorded for each subject. We will also do a sensitivity analysis using the PP analysis set, which is when we test how

robust our results are to different assumptions or scenarios.

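### The exclusion criteria name allergy to vitamin D but not to solifenacin, so a child with known solifenacin hypersensitivity can be randomized to it

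*Combined protocol and SAP*

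**What the plan says.** Section 4.2 contains a single allergy criterion: "Those have a history of allergy or allergic disease to vitamin D preparations". It also has a general clause, "Any condition that could cause urinary symptoms or interfere with assessment of efficacy parameters", and exclusions for chronic constipation, severe gastrointestinal disease and abnormal liver or kidney function. No inclusion or exclusion criterion mentions allergy to, hypersensitivity to, or a contraindication for solifenacin or anticholinergics.

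Section 5.1 makes solifenacin one of the two study drugs: "Children in the SOL+SU group will receive treatment with solifenacin succinate", at 5 mg once daily with a maximum of 10 mg per day. Section 6.2.2.3 states that "eligible participants will be randomized into one of three different intervention groups", so eligibility for the trial is eligibility for every arm.

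Screening follows the listed criteria. Section 6.2.1 describes patients "answering screening questions in a questionnaire (i.e., excluding exclusion criteria"), and section 6.2.1.2 adds that "These criteria will be confirmed at the time of enrollment through a questionnaire". The schedule in section 6.1 includes a medical history on Day 1.

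**The concern.** The plan treats allergy to a study drug as a reason to keep a child out, but for only one of its two drugs, and it gives no reason for the difference. A child who has already reacted to solifenacin passes the written criteria and can draw the solifenacin arm.

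Such children could plausibly present. Section 2 says that anticholinergics are commonly prescribed when symptoms persist despite urotherapy, and it places solifenacin in that class. Section 4.3 recruits from pediatric urology clinics, and nothing in sections 4.1 or 4.2 requires children to be untreated or excludes earlier anticholinergic use.

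What is at stake is the safety of the individual child, which would rest on the alertness of a clinician or family and not on the eligibility rule. The point is limited to known hypersensitivity. The anticholinergic side effects covered in section 7.1 are a separate matter.

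**Working it through.** The main check is textual: does any other provision keep this child from receiving solifenacin?

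| Provision | What it covers | Does it exclude known solifenacin hypersensitivity? |
|---|---|---|
| 4.2, allergy criterion | Vitamin D preparations | No |
| 4.2, catch-all | Causes of urinary symptoms; interference with efficacy assessment | Not on a natural reading |
| 4.2, organ and bowel exclusions | Conditions that may raise some solifenacin risks | No |
| 3 and 5.2, compliance | Poor compliance; completing treatment | No, not an allergy rule |
| 6.1, 6.2.1.1, 6.2.1.2: history, consent, record review | May reveal a past reaction | No rule makes it an exclusion |
| 6.2.1, 6.2.1.2: questionnaire | The listed criteria | Not required to ask |
| 7.1 and 8, discontinuation | Effects that appear on treatment | No, acts after the first dose |

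No row closes the gap. The plan states no figure on this point, so there is none to reproduce. The calculations below only give a sense of scale.

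**Chance of assignment.** Section 9.2 plans 97 per group, so I take 1:1:1 allocation. If k affected children are enrolled, the probability that at least one is assigned solifenacin is 1 − (2/3)^k:

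- k = 1: 1 − 0.667 = 33%
- k = 2: 1 − 0.444 = 56%
- k = 3: 1 − 0.296 = 70%

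The values of k are illustrative. The documents give no prevalence.

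**Effect on the primary result.** Section 9.2 also gives SD 5.0 and a target difference of 1.5 voids per day. Suppose solifenacin plus SU truly differs from SU alone by 1.5, and one child in the solifenacin arm receives no drug and gets no drug effect.

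- Share of the arm: 1/97 = 1.0%
- Shift in the arm mean: 1.5/97 = 0.0155 voids/day
- Standard error of a two-group difference: 5 × √(2/97) = 0.718 voids/day
- Ratio: 0.0155/0.718 = 2.2%

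Against SU alone, the shift is a dilution. Against vitamin D plus SU its direction depends on which drug is better: if vitamin D is superior, as section 9.1 expects, an untreated child in the solifenacin arm widens the contrast. The size is the same and negligible either way.

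**Analysis sets.** Section 9.3.1 compares groups as randomized, "regardless of what treatment they actually received or completed", so a child from whom solifenacin is withheld stays in the assigned arm for the primary outcome. The child could drop out of the per-protocol set used for the categorical outcomes (section 9.3.2). If no dose is taken, the child also leaves the safety set, which section 9.3.3 defines as "a subset of all patients who took at least one dose of the study drug" with safety records in the database.

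**The case against.** The strongest reply is that this is a drafting matter with no consequence for the trial's conclusions. Harm needs several things to go wrong together. The child must have had earlier exposure and a known reaction; it must be missed or ignored at the Day 1 history, the record review and the in-person consent discussion; the child must draw the solifenacin arm; and the drug must still be given. A family can also decline to take part. An investigator might stretch the catch-all to a child who cannot take one of the study drugs, or point to the expectations of compliance in sections 3 and 5.2. The screening questionnaire itself is not in the documents (section 15 reproduces only the symptom score), so what it asks is not known. Finally, the assumed numbers of affected children have no source.

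Much of this stands as a limit on size. The event is unlikely, the questionnaire items are unseen, and the probabilities for two or three children are illustrations only. None of it supplies the missing rule. The catch-all is framed around symptoms and efficacy, the compliance text is not an allergy criterion, and a reaction revealed at history or consent still leaves the child formally eligible. Section 4.2 does not leave vitamin D allergy to discretion, and the same treatment is due to the other drug.

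**Conclusion.** The concern holds. As written, the criteria admit a child with known solifenacin hypersensitivity to a trial in which, with equal allocation, that child has a 1 in 3 chance of being assigned the drug. This is a minor, avoidable safety omission. Few children are likely to be affected, because a known reaction requires earlier exposure, but the documents do not allow the number to be estimated.

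There is no material bias. Under the assumptions of a 1.5 voids/day drug effect, SD 5.0 and 97 per arm, one untreated child shifts the solifenacin mean by about 0.015 voids/day, roughly 2% of a standard error. The conclusion about eligibility depends on none of these numbers.

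**What to change.** In section 4.2, reword the allergy criterion to read: history of allergy or hypersensitivity to vitamin D preparations or to solifenacin. Add the matching item to the screening questionnaire. Apply it to every child before randomization, whatever the eventual arm, so that the three groups are drawn from the same population.

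The cost is a few words and one screening question. Loss of recruitment should be negligible, and the sample size and analysis do not change.

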4.3 Study Enrollment Procedures

Eligible participants will be selected from patients visiting the pediatric urology clinics at the Children's Hospital of Chongqing Medical University who have been diagnosed with OAB-dry and have serum vitamin D levels below 35ng/ml. The screening log will record reasons for both ineligibility and non-participation of eligible candidates. Prior to the commencement of intervention measures, interested patients will be required to provide informed consent.

5. STUDY INTERVENTIONS

5.1 Interventions, Administration, and Duration

During the eight-week treatment period, the study was divided into three intervention groups, and each patient received follow-up care from an outpatient physician every four weeks. Participants in each intervention group will be required to attend a 30-minute SU program per session.

Children assigned to the VDS+SU group will receive high-dose VDS (800 IU, three times per day) in addition to the biweekly SU course.

Children in the SOL+SU group will receive treatment with solifenacin succinate (5 mg once daily, with a maximum dose of 10 mg per day), in addition to the SU course.

Participants in the SU group only attend regular SU meetings, which provide basic information and an explanation of the disease, guidance on behavioral changes and lifestyle advice, registration of urinary habits using a bladder diary, as well as support and encouragement from caregivers.

5.2 Adherence Assessment

Upon enrollment, all participants will be required to complete all relevant intervention treatments, as well as subsequent questionnaire surveys and efficacy assessments, without any interruption to the intervention treatment.

6. STUDY PROCEDURES.

6.1 Schedule of Evaluations

Assessment	Enrollment: Day1	Run-in period (Day2-8)	Week 4 (Day 33- 39)	Week 8 (Day 61-67)
Informed Consent Form	\checkmark			

Efficacy and Safety of High-Dose Vitamin D Supplementation for Overactive Bladder Dry in Children: A Randomized Clinical Trial (Edition Number:3)

Demographics	\checkmark			
Medical History	\checkmark		\checkmark	\checkmark
SU	\checkmark		\checkmark	\checkmark
Bladder Diary		\checkmark	\checkmark	\checkmark
Current Medications		\checkmark	\checkmark	\checkmark
measurements of biochemistry.	\checkmark			\checkmark
measurements of hematology,	\checkmark			\checkmark
measurements of urinalysis.	\checkmark			\checkmark
Adverse Events			\checkmark	\checkmark

6.2 Description of Evaluations

6.2.1 Screening Evaluation

Eligible participants will be identified at the Outpatient Department of Urology, Children's Hospital of Chongqing Medical University. Patients will be further screened for eligibility by answering screening questions in a questionnaire (i.e., excluding exclusion criteria).

6.2.1.1 Consent Procedure

An informed consent form that describes the screening and study procedures will be used. The study coordinator will conduct the consent procedure in person. The coordinator will describe the study to potential participants. The study coordinator and the principal investigator will regularly review the informed consent form for potential modifications.

6.2.1.2 Screening

Before the interventions begin, a screening assessment must be completed to determine eligibility. Medical records will be reviewed to identify patients who meet the relevant inclusion criteria and do not meet any exclusion criteria. These criteria will be confirmed at the time of enrollment through a questionnaire.

6.2.2 Enrollment, Baseline, and/or Randomization

6.2.2.1 Enrollment

Participants who complete the eligibility screening, consent to participate, and provide an informed consent form for the study will be enrolled. Their contact information will be entered into the database.

6.2.2.2 Baseline assessment

All participants will have a 7-day run-in period during which children are asked to carefully record their OAB-dry symptoms. The purpose of this run-in period is to establish a baseline for evaluating the effect of the intervention measures investigated.

6.2.2.3 Randomization

After completing a comprehensive baseline assessment and meeting the eligibility

criteria, eligible participants will be randomized into one of three different intervention groups. To ensure the highest standard of allocation concealment, the randomization process of this clinical trial will be executed by a designed computer program developed by a project staff member who is not involved in the execution and statistical analysis of this study. The allocation will be securely hidden in sequentially numbered sealed envelopes, which will be entrusted to an inpatient doctor who is not involved in the trial.

6.2.3 Blinding

To minimize assessment bias and ensure the integrity of the study, we will implement rigorous measures to conceal group allocation and hypotheses from outcome assessors and statisticians. We will emphasize the importance of minimizing assessment bias to assessors and regularly review the blinding status to strictly maintain blinding. In addition, the data analyst will only be allowed to review coded data with participant names replaced by numbers.

6.2.4 Follow-up Visits

Patients will undergo regular follow-ups with an outpatient physician. Follow-up assessments will include measurements of urination frequency, urgency score, lower urinary tract symptom score, nocturia frequency, serum vitamin D levels, and other clinical laboratory parameters, such as hematology, biochemistry, and urinalysis.

6.2.5 Completion/Final Evaluation

The effectiveness of various intervention measures for pediatric OAB-dry will be evaluated by comparing changes in the primary urinary frequency and urgency scores between the intervention groups.

7. SAFETY ASSESSMENTS

This study includes clinical interventions, and the primary focus of safety evaluation will be on assessing the adverse effects and exacerbation of clinical symptoms after oral administration of the drug. Patients will be encouraged to report any related complications or adverse events directly to us.

7.1 Specification of Safety Parameters

Participants were required to take solifenacin and high-dose VDS as part of the study. Anticholinergic side effects, including dry mouth, blurred vision, constipation, and nausea, among others, may occur due to solifenacin use. If any of these symptoms occur, the medication will be discontinued, and the participant will be removed from the study. Over-supplementation of vitamin D can lead to symptoms of vitamin D toxicity, including anorexia, nausea, diarrhea, constipation, irritability, and somnolence. Any occurrence of these adverse drug reactions or serum vitamin D levels exceeding 100 ng/mL will be evaluated as unsafe.

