9.5 Outcomes and data Analyses

We will employ diverse measures to describe the characteristics of our data, depending on their nature. For numerical data that are continuous and can take any value within a range, we will use the mean (the arithmetic average of all values), the SD (a measure of how much the values deviate from the mean), the median (the central value when the data are sorted from the lowest to the highest), and the interquartile ranges (IQRs) (the range containing the middle 50% of data). For non-numerical data that are categorical and can belong to multiple groups or categories, we will use the frequency (the number of occurrences for each category) and the percentile (the proportion of data that falls below a specific value or category).

We will examine our data for any outliers or missing values that could influence our analysis. Outliers refer to values that differ significantly from the majority of the data and may indicate errors or exceptional cases, while missing values are data points that are unavailable or not recorded. Although we will employ effective data collection and management practices, missing values may still occur due to various factors.

To estimate the missing values for continuous data, we will use multiple imputation. This approach replaces the missing values with plausible estimates based on the other available data. We will assume that the missing values are missing completely at random, meaning that their occurrence does not depend on any variable, including their value. We will also conduct a sensitivity analysis to determine if the missing values affect our results or conclusions.

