9.5.1 Primary Outcome

The study aims to determine the primary outcomes of urinary frequency among three groups of participants. The frequency of urination will be recorded at three different points in time, i.e., when the participants enroll in the study, four weeks after starting the treatment, and eight weeks after starting the treatment. We will compare the frequency of urination between the groups at each time point, and assess changes in urination frequency from enrollment to four weeks after starting treatment. To record urinary frequency, we will use a bladder diary, and these outcomes will be considered continuous variables, with any positive integer value within a specified range.

To analyze the data, we will use the intention-to-treat approach to avoid bias from factors such as dropout or crossover. We will also handle missing data before analysis. Statistical tests will be applied to compare the groups based on data distribution and variance, which affects the reliability of results. For normally distributed data with homogeneous variance, we will use ANOVA, followed by post-hoc comparisons and Bonferroni correction to reduce Type I errors. We will report data changes using mean and SD and differences between groups using point estimation and 95% confidence intervals (95%CI).

For non-normally distributed data with heterogeneous variance, we will use the Kruskal-Wallis test to compare groups. Post-hoc comparisons between groups will be done using the Wilcoxon rank sum test, and p-values will be adjusted by Bonferroni correction. Data changes will be reported using median and IQRs, and differences between groups using the Hodges-Lehmann (HL) estimate of location shift and 95% confidence intervals (95%CI). P-values will also be adjusted for multiple comparisons to avoid false positives, and a two-tailed P-value less than .05 will be considered statistically significant.

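### Section 7.1 removes children from the study for side effects of a drug given in one arm, while section 9.5 assumes missingness unrelated to any variable; separately, two categorical outcomes are analysed per protocol only

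*Combined protocol and SAP*

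**What the plan says.** **Removal.** Section 7.1 of the combined protocol and SAP names dry mouth, blurred vision, constipation and nausea, among others, as possible effects of solifenacin. It continues: "If any of these symptoms occur, the medication will be discontinued, and the participant will be removed from the study". Section 5.1 gives solifenacin to the SOL+SU arm only. For vitamin D, section 7.1 says: "Over-supplementation of vitamin D can lead to symptoms of vitamin D toxicity, including anorexia, nausea, diarrhea, constipation, irritability, and somnolence". The stated consequence is different: "Any occurrence of these adverse drug reactions or serum vitamin D levels exceeding 100 ng/mL will be evaluated as unsafe". It does not mention removal. The SU arm has no study drug.

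**Stopping.** Section 8 stops the intervention for drug-related effects or worsening OAB symptoms, in any arm. It does not say whether the child also leaves follow-up.

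**Missing data.** Section 9.5 states: "To estimate the missing values for continuous data, we will use multiple imputation". It adds that imputed values will draw on the other data available, but names no model. The assumption is: "We will assume that the missing values are missing completely at random, meaning that their occurrence does not depend on any variable". It also promises: "We will also conduct a sensitivity analysis to determine if the missing values affect our results or conclusions". The content of that analysis is not given.

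**Analysis sets.** Section 9.3.1 defines intention-to-treat as comparison by assigned group, "regardless of what treatment they actually received or completed". For the primary outcome, section 9.5.1 says "we will use the intention-to-treat approach to avoid bias from factors such as dropout or crossover". Sections 9.3.2 and 9.5.2 place perceived improvement and satisfaction on the per-protocol set, with no intention-to-treat analysis of either.

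**The concern.** A rule that takes children out of the study for effects of a drug given in one arm makes missingness depend on arm and on adverse events. Section 9.5 assumes that it depends on nothing. No section keeps the later diaries of removed children, so the intention-to-treat analysis of voiding frequency would use imputed values for them.

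VDS+SU versus SOL+SU, the comparison with the active drug, and SOL+SU versus SU could be biased in either direction if removed children differ from completers in ways the imputation misses. If leaving under section 8 is also intended, loss for worsening symptoms is tied to the outcome itself and can occur in every arm. Diaries that were never collected cannot be recovered at the analysis stage.

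The per-protocol analysis of the two categorical outcomes is an independent matter. It gives up the randomised comparison whatever the removal rule means.

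**Working it through.** **1. The plan's own figures.** Section 9.2 gives a difference of 1.5 voids/day, SD 5.0, 87 per group, and 97 after 10% attrition. A three-group ANOVA with means 0, 1.5 and 3.0 has 95.05% power at 87 per group, and 87/0.90 = 96.7, which rounds up to 97. The spacing of the means is an assumption. The steps below use only the SD, the 87 and the 1.5.

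**2. Test scale.** The standard error of a pairwise difference is 5.0 × √(2/87) = 0.758. With Bonferroni over three pairs the level is 0.05/3 = 1.67%, so the critical value is 2.394. For a shift b with no true difference, the false-positive rate is P(|Z + b/0.758| > 2.394). This is a normal approximation with 87 per arm throughout.

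**3. Assumed inputs.** The documents give no removal rate, no difference between removed children and completers, and no timing. I take p = 10% or 20% of SOL+SU removed, differing from completers by d = 1.5 (the design difference) or 3 voids/day at weeks 4 and 8. The correlation among baseline, week 4 and week 8 is taken as 0.6.

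**4. Shift in the SOL+SU mean at week 8**

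- *(a) No week-8 diary, imputed like completers.* Shift = p × d: 0.10 × 1.5 = 0.15; 0.10 × 3 = 0.30; 0.20 × 1.5 = 0.30; 0.20 × 3 = 0.60. False-positive rates are 1.9%, 2.5%, 2.5% and 5.5%.
- *(b) All removed at week 4 with that diary kept, imputed within arm from baseline and week 4.* With all correlations 0.6, the week-4 coefficient is 0.6/(1 + 0.6) = 0.375, so 0.625 of d is missed. Shift = 0.625 × p × d = 0.09, 0.19, 0.19 and 0.38. False-positive rates run from 1.7% to about 3%.
- *(c) One third each removed before Day 33, at week 4 and at week 8.* Simulation gives 0.08, 0.15, 0.15 and 0.29, with rates up to 2.5%. This is less than (a) because some diaries survive.
- *(d) Week-8 diary kept for every removed child, or d = 0.* The shift is 0.

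The sign reverses if removed children do better than completers. A t-test simulation with 97 per arm that ignores removed children agrees with (a): at p = 20%, the rate is 5.5% with d = 3 worse (shift 0.60), 5.3% with d = 3 better (shift -0.59), and 1.4% with no difference.

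**5. If arm were left out of the imputation.** Assume both drug arms lie 1.5 below SU, with 97 per arm. At p = 10% the pooled completer mean is -1.5 × (97 + 87.3)/281.3 = -0.983, so SOL+SU moves toward SU by 0.10 × (1.5 - 0.983) = 0.05. At p = 20% it moves by 0.20 × (1.5 - 0.964) = 0.11.

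**6. Week 4.** Under section 6.1, diaries and adverse-event checks share the week-4 (Day 33 to 39) and week-8 visits. A child whose effect is found at week 4 may still supply that diary. A child who reports directly between visits, as section 7 encourages, and is removed before Day 33 has only the run-in diary. Week-4 comparisons are therefore affected only by children removed before the week-4 diary.

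**7. Per-protocol outcomes.** If a fraction a of an arm is outside the set and a proportion q within it is satisfied, the all-randomised proportion lies between (1 - a)q and (1 - a)q + a. With q = 70% (assumed) this is 63 to 73% at a = 10% and 56 to 76% at a = 20%.

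**The case against.** **Multiple imputation does not need data missing completely at random.** Section 9.5 bases imputed values on the other available data, which could naturally include arm, baseline and week-4 diaries. This stands. It makes step 5 and the upper end of (a) less likely. It does not settle the matter, because no variable is named and the stated assumption gives no reason to include arm.

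**The largest figure is a corner case.** The 5.5% needs 20% removed, a difference of twice the design value, no week-8 diary and no use of week-4 data. This also stands. Cases (b) and (c) give at most about 3%, and their mild ends are close to nominal.

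**Intention-to-treat is not abandoned.** Removed children stay in their assigned group through imputation. That is correct. The gap is that the comparison depends on an unspecified model for them.

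**Loss may not be one-sided.** Constipation and nausea appear in both lists in section 7.1, section 8 covers any arm, and section 9.1 anticipates similar safety profiles. Similar event rates would not balance the removal rule as section 7.1 states it. They could if section 8 also means leaving the study, but then VDS+SU versus SU is exposed too, and loss for worsening symptoms relates to the outcome.

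**The per-protocol issue is separate** and adds no weight to the primary-outcome point. I agree, and treat it so.

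**Conclusion.** The textual conflict is firm: removal under section 7.1 can make missingness depend on arm, and section 9.5 assumes that it cannot. As section 7.1 is written, two contrasts are exposed; if section 8 also means leaving the study, all three are.

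A reader might infer that the trial's result is biased, or biased in favour of vitamin D. The documents do not support that. They give no removal rates, the direction could go either way, and zero bias is possible. A reader might also infer that VDS+SU versus SU is safe. That holds only if stopping under section 8 leaves follow-up intact.

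On the assumed inputs, the week-8 shift is 0 to 0.60 voids/day against a design difference of 1.5, and 0.08 to 0.38 where some later diaries are used. The per-protocol-only analysis of perceived improvement and satisfaction stands as its own, secondary point. This should be fixed, mainly because the lost diaries cannot be recovered later.

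**What to change.** 1. **Follow-up.** Leave the clinical stopping rules to the investigators. Reconcile sections 7.1 and 8 with 9.3.1 and 9.5.1 so that stopping treatment is separate from leaving the study. Add that week-4 and week-8 diaries and questionnaires are still collected after treatment stops unless consent is withdrawn. In the simulated cases, week-8 diaries from a random 70% of removed children, with discontinuation in the imputation model, brought the shift to 0.00 in all four combinations of p and d.

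2. **Missing data, section 9.5.** Replace missing completely at random with multiple imputation under missing at random. Include arm, baseline voids, week-4 voids and, where off-treatment data exist, discontinuation status. Define the sensitivity analysis as a delta adjustment by arm, in both directions, over a range set in advance.

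3. **Categorical outcomes, sections 9.3.2 and 9.5.2.** Make intention-to-treat the main set for perceived improvement and satisfaction, with missing responses imputed. Keep per protocol as supportive, and state whether a child stopped under section 7.1 or 8 belongs to it.

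The cost is protocol and SAP wording, a small burden at visits already scheduled, and modest extra analysis work.
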